3.0 OUTCOMES AND MEASURES

Primary outcome: psychotic symptoms measured by PANSS total score.

Secondary outcomes: symptom distress, mood, functioning/social functioning; drug use frequency; perceived criticism; medication adherence; user-empowerment; well-being; quality of life; recovery; service and health economic measures. Treatment domains will also be measured via daily ambulatory-monitoring outcome assessment questions in the Actissist group. We will also collect demographic information and mobile and app usage rates.

A trained research assistant will undertake the following participant assessments in both Actissist and ClinTouch groups at baseline, 12 weeks and 24 weeks post-randomisation. Measures have been selected which map directly onto hypothesised mechanisms of change as well as known predictors of relapse.

Primary Outcome Measure

1. Mental Health Status: The Positive and Negative Syndrome Scale, PANSS, (Kay et al, 1987) is a valid and reliable 30-item rating scale subdivided into three symptom categories: positive symptoms (e.g. Delusions, hallucinatory behaviour), negative symptoms (e.g. blunted affect, emotional withdrawal), and general symptoms (e.g. anxiety, tension).

Note: Participants that may join Actissist having recently completed involvement in a research study that included the PANSS assessment at final follow up, plus additional questionnaire measures in common with the baseline for Actissist, will be advised that **with their written consent**, the Actissist team will request these data from their final follow up on previous study. If the participant agrees, then only the additional secondary outcome measures in the following section will be completed.

Secondary Outcome Measures

We will also assess changes in symptoms, substance use, emotional distress, recovery, quality of life and well-being, service / app engagement and health economic indices.

- (i) *Mental Health Status:* The Psychotic Symptoms Rating Scales (PSYRATS; [name] et al., 1999) is a well-validated assessment of the frequency and intensity of hallucinations and delusion in people with psychosis. The PSYRATS is typically administered as a semi-structured interview. It is typical to administer the PSYRATS items within the PANSS semi-structured interview to aid in the scoring of the PANSS items P1 Delusions and P3 Hallucinatory behaviour, consequently the (formal) administration of this measure will not necessitate additional participant time. The Calgary Depression Scale for Schizophrenia (CDSS; Addington, Addington, & Schissel, 1990) is a well validated assessment of depressive symptoms in people with psychosis. The CDSS is typically administered as a semi-structured interview. It is typical to administer the CDSS items within the PANSS semi-structured interview to aid in the scoring of the PANSS item G6 Depression, consequently the (formal) administration of this measure will not necessitate additional participant time. The Personal and Social Performance Scale (Morosini, Magliano, Brambilla, Ugolini & Pioli, 2000) is a brief interview measure of social functioning thought to be easier to administer than other traditionally used measures. Excellent psychometric properties were reported in the original validation article. Perceived criticism scale (Hooley & Teasdale, 1989) is a measure of perceived criticism by a significant other. This scale was adapted by Schlosser and colleagues (2012) to create the perceived criticism and perceived warmth scale. Seven items are rated using a 1 (not at all critical) to 10 (very critical) scale. Previous research suggests that the PCPW scale has good predicative validity and is not correlated with current symptoms of depression or anxiety. It takes approx. 3 minutes to complete. Recovery will be measured using The Questionnaire about the Process of Recovery QPR (Law, Neil, Dunnn & Morrison, 2014) is a validated measures of recovery in psychosis. The Warwick-Edinburgh Mental Wellbeing Scale (WEMWBS; Tennant, et al., 2006) is a measure of well-being and has been validated with users of mental health services.
- (ii) *Substance use measures:* Time Line Follow Back for drugs and alcohol (TLFB; Sobell & Sobell, 1992) is an assessment method that obtains estimates of daily alcohol and other drug use and has been evaluated with clinical and nonclinical populations. Participants provide retrospective estimates of their daily cannabis use over a specified time period (3 months). The TLFB will be administered at baseline, 12 weeks and 24 weeks post-randomisation. Additionally, participants will be asked to complete the Alcohol, Smoking and Substance Involvement Screening Test (ASSIST; World Health Organisation Working Group, 2002) at baseline, 12 weeks and 24 weeks post-randomisation to identify changes in general drug after the

intervention period. To characterise the sample, participants will be asked to complete the Alcohol Use Disorders Identification Test (AUDIT; Babor et al., 2001) at baseline. The AUDIT contains 10 self-report items about alcohol-related experiences and has been well validated for use in clinical research. The original AUDIT records alcohol consumption over the past 12 months; however, this is regularly amended in trials to 3 months for the purposes of follow-up assessments. Therefore, the AUDIT will be administered to measure alcohol consumption over the past 3 months at baseline, 12 weeks and 24 weeks post-randomisation to identify any changes in alcohol consumption. The Cannabis Use Disorders Identification Test-Revised (CUDIT-R; Adamson et al., 2010) will be used to measure cannabis use over the past 3 months at baseline, post-treatment and follow-up. The Drug Use Disorders Identification Test-Extended (DUDIT-E; Berman et al., 2007) will also be administered at baseline, 12 weeks and 24 weeks post-randomisation for cannabis use only to explore perceptions of drug use and treatment readiness.

- (iii) *App Engagement*: A quantitative feedback questionnaire will be given to service users at the end of the study to collate their opinions on the usefulness of the technology. The user version of the Mobile Application Rating Scale (uMARS; Stoyanov, Hides, Kavanagh & Wilson, 2016) is a reliable method to assess the quality of mobile health (mHealth) apps and will measure the quality of both the Actissist and ClinTouch apps. The Quantitative Feedback Questionnaire (QFQ; Ainsworth et al., 2013) was developed to assess the acceptability and feasibility of utilising the ClinTouch app within a service user sample. The QFQ consists of 22 items pertaining to the integration of the technology into the daily routine and methodological reactivity and a further 10 questions enabling the participant to give their views on using the app they were allocated to. The mobile Agnew Relationship Measure (m-ARM; [name] et al. in press) will measure therapeutic alliance with the apps. Whilst all other measures will be paper-based, the m-ARM will be delivered at two points during the intervention period (month 1 and month 2) via a text message link. This will allow participants to complete two assessments of therapeutic alliance on a secure University of Manchester-managed survey site without the burden of a researcher visiting them to complete the assessment at two different timepoints. Only participants' unique study ID will be entered into the m-ARM survey database. At the end of the intervention period these data will be analysed by a PhD student member of the research team using factor analysis to shorten and refine the measure. This analysis will help to establish 'user acceptability' of the app and inform its further development, e.g., improving personalization.

- (iv) *Health Economics*: Euro-QoL Five Dimension (EQ-5D-5L; EuroQol group, 1990) is a measure of health status and preference for different health status. It is a self-rated descriptive system with five dimensions: mobility, self-care, usual activities, pain or discomfort, and anxiety or depression. Patients respond by describing they have no problems, slight problems, some problems, severe problems, extreme problems or that they are unable to do the activity. While the EQ-5D-5L is very commonly used in the UK context, its sensitivity and appropriateness in people with schizophrenia has been questioned (Brazier et al., 2014). The Client Service Receipt Inventory (CSRI; Beecham & Knapp, 2001) measures service utilisation, income, accommodation and other cost-related variables.
- (v) The Empowerment Rating Scale, ERS, (Rogers et al, 1997) is a 28-item scale designed to measure empowerment in users of mental health services. It takes around 15 minutes to self-administer. It shows good internal reliability (Cronbach's Alpha = 0.86). Item examples include, 'I am often able to overcome barriers,' and, 'I have a positive attitude about myself'.
- (vi) The Internalised Stigma of Mental Illness Inventory (ISMI; Ritsher, 2003) is a 29-item scale designed to measure internalised stigma in individuals with mental health problems. The scale has been validated in a wide range of clinical samples, including psychosis, and has demonstrated high internal consistency, test-retest reliability and construct validity.
- (vii) The eHealth and mHealth Interest Survey (EMIS) has been developed by the research team and is based on the findings obtained from the qualitative studies administered in the proof-of-concept trial. Service users in the Actissist 2.0 trial will be asked to complete the survey during the app set-up visit to minimise burden. Service users who are not in the Actissist trial will be asked to complete the surveys and then return them to the research team via their care coordinator or the CSO. Alternatively, a link to the survey will also be made available for participants to complete the survey online using the secure RedCap website. The survey contains 55 questions relating to technology ownership, use and interest and takes approximately 20 minutes to administer.
- (viii) The eHealth and mHealth Interest Survey - Clinician Version (EMIS-CV) has been developed by the research team based on findings obtained in focus groups with staff working in early intervention services in the proof-of-concept trial. Staff working in both primary and secondary health care services will be asked to complete either an online or paper-based version of the EMIS-CV. The survey contains 26 questions to elicit staff perceptions of service user technology ownership and engagement and

views towards the use of digital tools for early psychosis and takes approximately 8 minutes to administer.

(Total administration time - approx. 90 minutes).

Qualitative measures.

Individual qualitative interviews will comprise semi-structured in-depth interviews following an interview schedule. Staff will be asked to provide qualitative information following beta testing in Phase 1 about the usability of the app and a further sample of around 15 Trust staff whose client's participated in the trial will be interviewed to explore acceptability and usability of Actissist 2.0. Following the 12 week post randomization follow up assessment, >20 exit interviews (across both groups) with trial participants will be performed. A purposive sample will be sought to ensure maximum variation of sample and to elicit a broad range of views. This will include a balance of participants who have had a good outcome, those who have dropped out of the intervention or who refused participation, and control participants (specific interview guides have been developed for each group). The invitation to participate in a qualitative interview will be offered to the participants sampled for this stage of the study by a blind member of the research team; a mutually convenient date/ time will be agreed with the participant for the researcher to conduct the exit interview. Interviews will explore participants' experiences and expectations of the app, participants' views on the content, duration and intensity of the app (particularly focusing on perceptions of usefulness, engagement with the technology and facilitators/barriers to implementation), the role of mHealth apps within psychiatric management and self-management, perceived benefits of the app, disappointments/concerns and ongoing support needs. Participants who decline the trial will be invited to have a single time-point interview to explore views and experiences of current care and potential use of technologies such as mobile phones in mental health care. Interviews with participants who decline to participate in the trial, but would still be willing to take part in an interview, and with participants who withdraw early from the trial will be conducted at a time and place convenient for the participant or via the telephone, depending on participant preference.

3.1 Software systems, interface and compliance with NHS security standards.

The three general principles of information security (confidentiality, integrity and availability) will be followed in the implementation of Actissist and ClinTouch. All data transmitted to and from the app servers will be encrypted over https with strong ciphers as detailed in the Approved Cryptographic Algorithms Good Practice Guidelines (NHS, 2012). Cipher Suites will be implemented in compliance with Section 6 ("Preferred uses of cryptographic

algorithms in security protocols”) of the Good Practice Guidelines. In cases where participant data is downloaded from the Actissist or ClinTouch sites, these data will be securely encrypted with a pass phrase of appropriate length and complexity. Data transfers are secured by using standard web security protocols (TLS). Uploading data to a central server in real-time enables study data to be captured and so protects against data loss such as a phone be lost or stolen and removes the need for personal data storage on the device. The purpose of the server in this case is secure data storage.

Additional security measures.

There are a number of technical measures we will employ to protect personally identifiable data. Any data stored on the phone by the participant will be encrypted (AES-256). We will also recommend that participants set a passcode to access their smartphone. All smartphones provided by the research team will require a passcode for access. By using the ClinTouch real-time data capture capability, we will be minimising the storage of confidential data on the smartphone as data will be wirelessly uploaded to a secure server (keeping identifiable data stored on the phone to a minimum). All participants recruited in the study will give their informed consent, and this will include the risks of data security. These measures should be sufficient to prevent unauthorized data access, should the phone be lost or stolen.

4.0 Intervention

Actissist Intervention. The Actissist intervention is grounded in the cognitive maintenance model of psychosis, which proposes that cognitive appraisals contribute to the emergence of unhelpful beliefs and influence the interpretation of psychotic experiences. Specific functions of the app are informed by cognitive behaviour therapy (CBT) content described in various published academic works and by the views and insights from research with service users and EIS clinicians, expert clinical academics and software engineers during the Actissist proof-of-concept study. The Actissist app targets five domains: perceived criticism; socialisation; cannabis use; paranoia; and distressing voice-hearing. Medication adherence is monitored on a weekly basis. The Actissist app works as follows: the app emits an alarm prompting participants to access the app at 3 pseudo-randomised time points per day, 6 days a week between the hours 10 am to 10 pm (or at the patient's preferred time) for 12-weeks alongside usual treatment. The prompts serve as a reminder to use the app and requests that the participant accesses one/more of the target treatment domains (if applicable). Participants can either snooze (for up to 30 minutes) or decline interacting with the app at any given alarm alert. Participants can also self-initiate use, providing them with the flexibility to engage with the app as and when required. Participants complete a series of self-assessment questions that are structured as question-answer exchanges, which are

then followed by normalising messages and cognitive and behavioural strategies for managing distressing experiences. There are multiple messages associated with each branched response to minimise boredom and repetition within the app. In addition to the self-assessment questions, participants can access multi-media material, including audio relaxation and mindfulness exercises, patient recovery stories, an open diary, mental health fact sheets, external links to web-related content (e.g. Technology, Entertainment and Design (TED) talks, useful websites), and a graphical summary of data points entered for each domain accessed. The multi-media material is contained within the app. At its simplest, the multi-media repository can contain a list of URLs to content on the web, and so the management of this section of the app is akin to managing a list of favourites or bookmarks in a web browser. Managing this type of content requires a similar level of expertise to managing a Facebook page, for example. Users can also customise the aesthetics of the app. During the initial consultation with the researcher at the app set-up session, patients will be trained on using the app and how to navigate through the app. Akin with CBT principles, the researcher will invite each participant at the app set-up session to choose a goal to work towards over the intervention period. Progress towards the goal will be monitored and reviewed fortnightly within the app.

The multi-media material (MMM) is contained within the app, and the app will provide an interface for adding, modifying and deleting RPMM content. At its simplest, the MMM can contain a list of URLs to content on the web, and so the managements of the RPMM are akin to managing a list of favourites or bookmarks in a web browser. The MMM will also allow multi-media content from the smartphone's local storage to be added such as photos or music. We envisage that managing this type of content will require a similar level of expertise to managing a Facebook page.

ClinTouch (control) condition: ClinTouch triggers, collects and wirelessly uploads symptom and mood data to a server 6-days/week for 12-weeks. Participants indicate the degree to which they agree/disagree with 14 symptom-statements since the last entry. As per the Actissist condition, mobile handsets will emit an alarm at 3 pseudo-random times of the day, with a 'snooze' option available if participants are occupied.

A research assistant will train participants in how to use the software. Software will be pre-loaded on a loaned smartphone or downloaded on the participant's own smartphone. Safety concerns will be managed in close consultation with participants' care co-ordinators and emergency contacts are clearly available on both apps.

For both conditions, a trained research assistant will train participants in how to use the software. For both Actissist and ClinTouch, participants will view written 'in-app' instructions and a printed hard copy of instructions on how to use the app. Software will be pre-loaded on a loaned smartphone or downloaded on participant's own smartphone. The project officer will phone, text or email (depending on participant preference) all participants at weeks 1, 2 4, and 8 to check the app is working smoothly and remind participants to charge the device, alert the participant to the receipt of the mARM survey (in weeks 4 and 8), and in week 11 to book a date for follow-up assessments. Concerns will be managed in close consultation with participants' care co-ordinators and emergency contacts will be clearly available in the menu options on both apps.

5.0 Data collection, management and analysis

Data Collection Methods

All outcome measures will be administered at baseline and subsequently at 12 weeks and 24 weeks post-randomisation by RAs who will have been trained in the use of all the instruments and scales, to achieve a satisfactory level of inter-rater reliability. Accuracy in administering and scoring the PANSS at baseline and at the 12 and 24 week follow up stage is critical in order to detect any change that might be attributable to the app the participant used. To ensure that important details aren't missed, the PANSS assessments will be digitally recorded using an encrypted device to enable our research team to review participants' responses when scoring the assessment. Recordings will be downloaded to a secure server on return to the office and deleted at the end of the study once reliability of rating has been assured. Regular training sessions including the use of role play will be conducted with all research assistants in order to maintain reliability and prevent rater drift. Participants will be offered choices regarding length of assessments, including the option of breaks and multiple occasions. The option to conduct the PANSS assessment over the telephone at 12 and 24 weeks post-randomisation will be offered to participants whose circumstances may have changed since baseline assessment, e.g., they are now working. Assessment measures will be clearly prioritised so that the most important will be collected first to avoid missing data. We will have a standard protocol for managing any distress that is associated with the completion of measures, which we have successfully utilised in several trials and has been developed in collaboration with service users (Appendix 1).

Note: for participants recruited to Actissist, who give written consent for their most recent PANSS, and other questionnaire data collected at final follow up in their previous study that is common to the Actissist baseline to be shared by their previous study team, the time taken for the completion of the baseline measures will be substantially reduced.

Protection Against Bias

Our assessment of the primary outcome will be blinded. Blindness of raters is ensured using a variety of procedures, including briefing participants prior to assessment not to disclose their allocation and data protection of randomisation information. RAs will remain blind to group allocation. An RA who did not conduct the phone set up session will conduct the follow up assessment to maintain the blind. The project officer, or a member of the research team independent to the follow up procedure, will book follow up appointments to further ensure blinding is maintained. Unblindings will be regularly monitored and recorded. Deliberate unblinding would only occur in the case of a serious adverse incident such as risk towards self/others by a participant. The statistician will be blinded during the analysis by withholding the identity of the randomised groups and only once the analysis is completed and interpreted will these be revealed. Due to the nature of the intervention, all participants will be unblinded and fully aware of their allocation to the intervention or control groups.

Randomisation Process

The randomisation process will be conducted by a remote internet based randomisation service (www.sealedenvelope.com). The allocation sequence will be developed using a computer random number generator to allocate participants on a 1:1 ratio, stratified by service (early intervention vs community mental health).

Once the eligibility of a patient has been confirmed and informed consent has been obtained, the researcher will assign a unique identification number to the patient and send this to the project manager. Having accessed the randomisation website, the project officer will enter only the identification number into the randomisation service, submit this information, and the next treatment allocation will be revealed on screen. Participants will then be informed of their allocation status. An email confirmation of the identification number, the allocated treatment and the date and time of randomisation is sent to the project officer. We have previous experience of using web-based randomisation in this setting, and do not anticipate any practical issues arising in this study. The randomisation list will be kept by the remote randomisation service (www.sealedenvelope.com), and kept separate to the collection of outcomes on the study database. The randomisation list will only be revealed to the researchers once all the recruitment is completed.

Data Management

Each study participant will be assigned a unique trial identification number at the start of the assessment process. This number will be written on all clinical assessment forms/datasheets

and databases used to record data on study participants. A hard copy of a record sheet linking patient identity, contact details and trial identification number for all participants will be kept at each site. It will be placed securely in a locked filing cabinet separate from datasheets. The local study coordinator will enter the data on to an electronic database, and all such data will be checked for errors before being transferred to the appropriate statistical package. All data will be kept secure at all times and maintained in accordance with the requirements of the Data Protection Act and archived according to clinical trial Good Clinical Practice (GCP) regulations.

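### The protocol neither keeps the app-rating questionnaires away from the blinded PANSS raters nor requires the PANSS score to be locked before those raters can see them

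*Protocol*

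**What the plan says.** Section 5.0 (Data Collection Methods) states: "All outcome measures will be administered at baseline and subsequently at 12 weeks and 24 weeks post-randomisation by RAs". Section 3.0 makes the same assignment: "A trained research assistant will undertake the following participant assessments in both Actissist and ClinTouch groups at baseline, 12 weeks and 24 weeks post-randomisation". The secondary outcomes introduced there include "quality of life and well-being, service / app engagement and health economic indices".

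Under App Engagement, Section 3.0 lists:
- the uMARS, a user rating of the quality of either app, with no time point given;
- the QFQ, with 22 items on daily routine and reactivity, plus "a further 10 questions enabling the participant to give their views on using the app they were allocated to". The feedback questionnaire is timed to the end of the study, with no visit and no administrator named;
- the m-ARM, sent by text-message link at months 1 and 2. All other measures are on paper.

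On blinding, Section 5.0 (Protection Against Bias) says "RAs will remain blind to group allocation". Its safeguards are a separate rater ("An RA who did not conduct the phone set up session will conduct the follow up assessment to maintain the blind"), "briefing participants prior to assessment not to disclose their allocation", appointments booked by someone outside the follow-up assessment, and a record of unblindings. Section 5.0 also takes measures in order of priority, and records PANSS interviews so that the team can go back over participants' "responses when scoring the assessment".

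Section 8.0 (Confidentiality, other study data) lists the RAs among those with direct access to paper records.

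**The concern.** The primary outcome, PANSS total score, is rated by an interviewer, and participants know their allocation. Rater blinding is therefore its main protection against bias.

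The two apps are easy to tell apart from a description. According to Section 4.0, Actissist offers CBT-based coping messages, relaxation audio, recovery stories, a diary and goal review. ClinTouch is described as collecting symptom and mood ratings. A participant's opinion of the app could readily show which one was used.

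The plan also pulls in two directions. Participants are briefed not to reveal their allocation, and then, on the default reading, the same RA collects a form asking about the allocated app. If a rater learns the arm before a PANSS score is settled, expectation can enter the score, and adjusting for baseline PANSS would not remove it.

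**Working it through.** This is mainly a question of procedure, so the sections are set side by side. A short calculation then shows why even a small bias would matter.

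**1. Who collects the forms.** Sections 3.0 and 5.0 give the listed outcome measures to RAs, and Section 2.0 (Method) has a blinded researcher collect outcome data. No section gives the uMARS or QFQ to anyone else. The m-ARM is handled separately, but the stated reason is to spare participants a researcher visit, not to protect the blind. RA collection is therefore the default reading, though it is not stated outright.

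**2. Whether the content can reveal the arm.** The ten QFQ questions on the allocated app could. The other 22 QFQ items and the uMARS scores need not.

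**3. Whether raters can see the answers.** Section 8.0 gives RAs access to paper records. Nothing seals these forms or stores them apart.

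**4. Whether PANSS scoring is finished first.** Taking measures in priority order suggests that the PANSS interview comes first within a visit. That orders collection and does not lock the score. Because recordings may be consulted during scoring, scoring can end after the visit. If an app rating is taken at 12 weeks, the order within the visit does nothing for the 24-week PANSS when the same RA rates both. The rule on separate RAs divides set-up from follow-up, not 12 weeks from 24 weeks, and Section 7.0 lists only three RAs.

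**5. Whether the stated safeguards cover this route.** The separate set-up RA, the briefing and the independent booking all address other ways of learning the arm. Recording unblindings documents a breach after it has occurred.

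**6. Illustration of what is at stake.** Inputs from Section 2.0 (Sample size calculation): difference 6 points, SD 15, baseline correlation 0.6, two-sided 5% level, 80% power, 63 per group, 85 recruited per group, 20% loss.

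- SD after baseline adjustment: 15 × √(1 − 0.6²) = 12.
- The plan's own figure: n = 2 × (1.960 + 0.842)² × 12² / 6² = 62.8, so 63 per group. This reproduces.
- Completers: 85 × 0.80 = 68 per arm (136 in total).
- Standard error of the difference: 12 × √(2/68) = 2.06 points.
- With no true effect and a net between-arm rating bias b, the rejection probability is 1 − Φ(1.96 − b/2.06) + Φ(−1.96 − b/2.06).

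| Assumed net bias b (PANSS points) | Two-sided type I error |
|---|---|
| 0 | 5.0% |
| 0.5 | 5.7% |
| 1 | 7.7% |
| 2 | 16% |
| 3 | 31% |

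The values of b are assumptions. The protocol gives no basis for choosing among them.

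**The case against.** The strongest reply is that the protocol never says RAs administer the uMARS or QFQ. The general sentence in Section 5.0 cannot be literal: an app cannot be rated at baseline, the m-ARM goes by link, the EMIS is completed at the app set-up visit, and the EMIS-CV goes to staff. The feedback questionnaire has its own timing rule and is handed to participants on paper. Section 5.0 (Data Management) gives data entry to the local study coordinator, so the rater need not read the forms. The PANSS is likely to be taken first, any unblinding is recorded, and no section says that the same RA rates both follow-ups.

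Much of this stands, and it limits what can be claimed. A reader might infer that the plan itself discloses allocation to the rater before PANSS scoring is final. The documents do not support that, because collection by RAs is a default reading, disclosure is an inference, and neither the visit nor the time of scoring is stated. A reader might also express the bias as a share of the 6-point target, apply it to all 136 expected completers, or assume that it favours Actissist. The protocol supports none of these: it gives no size or direction for rater bias and no proportion of raters unblinded.

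The reply does not close the gap. Nothing reassigns the forms, keeps them from RAs who can open the paper records, or locks the score first.

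**Conclusion.** The concern holds as a gap in protecting the blind. Read together, Sections 3.0, 5.0 and 8.0 leave the QFQ, and possibly the uMARS, by default with the RAs who must stay blind. The timing of these forms relative to PANSS scoring is open, and no safeguard is directed at this route. It should be corrected, because the exposed outcome is the primary one and the remedy is already within the trial's means.

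Confidence is moderate. The conclusion rests on the default reading of who collects the forms, on answers about the allocated app being informative, and on either scoring that ends after the visit or one RA rating both follow-ups. The size and direction of any bias are unknown. The rise in type I error to about 8 to 16% for a net bias of 1 to 2 points shows sensitivity and is not an estimate.

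**What to change.** Amend Section 3.0 (App Engagement) and Section 5.0 (Data Collection Methods) as follows:

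- Exempt the uMARS and QFQ from administration by RAs.
- Deliver both by the secure survey link already used for the m-ARM, or through the project officer, who already knows allocation from running the randomisation.
- State the visit at which each is given.
- State that outcome RAs do not see any app-specific response until that participant's 24-week PANSS score is locked. If paper is kept, file these forms apart from the records that RAs can open.

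The cost is protocol wording and two more questionnaires on an existing survey platform. Completion of the app ratings may be slightly lower than with a researcher present.
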